## 8.7 Benchmark reports

The benchmark reports are a comparison of one single unit (site or country) to the entire group of all other participating units. These benchmark reports are designed to be used as quality control for the participating sites and to describe country differences. Benchmark reports will be provided for:

- Participating site vs. all other sites
- Participating country vs. all other countries

The BAS will be the analysis population. Statistical reports (descriptive statistics) will be provided including all parameters from Baseline, First documented procedure, Additional procedure, GFU and 12MFU, but due to data protection no data from the Adverse Event form. The benchmark reports will be listed in tabular form and, depending on the variable type, the statistical output will include numbers and percentages, mean  $\pm$  SD, Odds ratio with 95% CI for all available parameters.

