If the patient appears in the participating medical center within 12 - 14 months after the index procedure, the “in hospital 12 months FU” CRF should be completed. If an “in hospital” visit does not occur after 13 months post index procedure, the site should apply all efforts to conduct interview by phone and document it in “12 months phone FU” CRF. The phone FU interview does not replace a medical checkup for the patient and serves as data collection, only.

Data to be collected during 12 months FU includes arrhythmia assessment, diagnostics, symptoms, hospitalization and re-ablations occurred since last visit, medications, QoL questionnaire.

To ensure a unified approach and to minimize possible bias, all sites will be trained to use the standardized “patient questionnaire for phone FU” with questions regarding parameters of interest equivalent to eCRF variables. In Germany, the phone FUs can be performed by Institut für Herzinfarktforschung, GmbH.

If study personnel obtain information during the phone FU that patient will appear in the hospital before the end of FU window, it is under site consideration to complete „12 months phone FU” CRF or conduct a medical check -up and complete „in hospital 12 months FU”.

Study Exit

Prior to exiting a patient from the study, it is recommended to follow the patient until all ongoing reportable AEs are resolved or unresolved with no further actions planned. Upon exiting from the study, no further study data will be collected or study visits will occur for the patients. All data available through the time of the subject’s exit will be used for analysis.

Patients are urged to remain in the study until the end of individual follow up but may be exited from the study for any of the following situations:

- Patient lost to follow up
- Patient chooses to withdraw (e.g., consent withdrawal, relocation to another geographic location)
- Investigator deems withdrawal necessary (e.g., medically justified, , failure of subject to maintain adequate study compliance)
- If patient were enrolled with the intention to perform Phased RFA, but get ablation with another technology
- Death

If patient has enrolled into study and vascular access was obtained with the intention of completing the study Phased RFA, but the subject did not receive any ablation energy, or complete entire study

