7.2.1 Frequency of Follow up

Data collection will be completed following standard of practice procedures at each participating site. Most of the sites have a standard of care for post AF ablation visits to invite patients for the medical checkup after the "blanking period" which is lasts around 3 month after the ablation procedure; some sites also see patients at 6 and 12 months after the Phased RFA.

To mitigate variations in clinical care practices for analysis, the visit windows below are proposed to aligning with typical care practices for this therapy. Data analyses will include follow up visits, regardless of when they occur.

Table 7-2: Follow Up Visit Windows

| Months | Window Starts (days post procedure) | Target (days post-procedure) | Window end (days post-procedure) |
|-----------|-------------------------------------|------------------------------|----------------------------------|
| 3 months | 85 | 90 | 100 |
| 6 months | 175 | 180 | 190 |
| 12 months | 351 | 365 | 425 |

Additional data collection activities may be completed using sub-studies under the GOLD AF Registry protocol. Sub-studies may be developed to satisfy local data needs and/or evaluate additional areas of scientific interest. Sub-studies must be reviewed and approved by Medtronic and will be documented and managed under separate cover.

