## 8.1 Statistical analyses for the main objective

### 8.1.1 Estimate Phased RFA 12 month success rate

Success rate estimated as the time to first AF re-occurrence event from the first documented procedure. Data about AF events will be collected since the first documented procedure, including 90 days of the "blanking period" and closes at 12 months FU. If no AF events occur during the follow-up period (considering the "blanking period") up to 12 (+2) months, the case is considered to be "event-free". Calculations will be done for exact 12 months (351 days) after first documented procedure.

Main objective will be calculated for the BAS, FAS and EFAS (see chapter 4 and Appendix B). A successful first documented procedure (successfulness by PVI confirmation) is the basis to calculate the main objective. Patients with a procedure during the "blanking

---

 in the service agreement #2 refers to the final report, which is one and the same document for this study

period" of 90 days after first documented procedure will be excluded from main objective calculations.

Predefined AF re-occurrence definition from CIP Version 2.0 will not be applied to calculate the main objective. Further analysis might be used to estimate Phased RFA success rate considering (re-)occurring left Afl events.

AF re-occurrence event defined as:

- AF pharmacological and/or electrical CV
- AF more the 30 sec on ECG/EGM
- AF less than 30 sec in combination with AF symptoms
- Re-ablations for AF

For this analysis adjudicated AE data and coded AE data (free text fields) will be used. AF re-occurrence event rate will be estimated with and without the use of antiarrhythmic drugs at time of the 12 month follow-up. AF re-occurrence rates will be calculated for patients from BAS and FAS (Appendix B) which need to have a signed 12 month FU / 12 month FU by phone form by definition. AF re-occurrence is defined as the first event of AF re-occurrence event and their related date information based on the following eCRF forms and data fields:

**Table 4:** Main objective variables at 12MFU / General FU form

eCRF field	Related date field	Related FID's annotated eCRF (V1.3, V1.4)
Reason for visit: AF re-occurrence	Date of visit	F11000050 F11000010
Re-ablation reason: Due to AF- occurrence	Date of visit	F11000070 F11000010
History of arrhythmias since last visit: AF	Date of first occur- rence	F12000012 F12000050

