## 8.6.2 Analysis of comparison groups

Group comparison will be provided including non-parametric statistical tests and odds ratios with 95% CI (two-group comparison) for all parameters. In Appendix D descriptive reports are listed.

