## Appendix B: Analysis tables, Study objectives and Analysis sets

eCRF SEGMENTS	eCRF CHAPTERS/ANALYSIS TABLES	STUDY OBJECTIVES	ANALYSIS SETS FOR INTERIM ANALYSIS	ANALYSIS SETS FOR FINAL ANALYSIS
BASELINE	Enrolment		APS, BAS	APS, BAS, FAS, EFAS
	Indication/Admission		APS, BAS	APS, BAS, FAS, EFAS
	Demographics		BAS	BAS, FAS, EFAS
	History of CVD		BAS	BAS, FAS, EFAS
	History of AF		BAS	BAS, FAS, EFAS
	Symptoms		BAS	BAS, FAS, EFAS
	Concomitant Diseases		BAS	BAS, FAS, EFAS
	Diagnostics		BAS	BAS, FAS, EFAS
	Medications List		BAS	BAS, FAS, EFAS
	AFEQT		BAS	BAS, FAS, EFAS
	Anticoagulation (before/during first documented procedure)	ANCILLARY OBJECTIVE	BAS	BAS, FAS, EFAS
FIRST DOCUMENTED PROCEDURE	Administrative information		APS, BAS	APS, BAS, FAS, EFAS
	Procedure summary information	ANCILLARY OBJECTIVE	BAS	BAS, FAS, EFAS
	Consumables		BAS	BAS, FAS, EFAS
	PVI confirmation		BAS	BAS, FAS, EFAS
	Hospital discharge		APS, BAS	APS, BAS, FAS, EFAS
	Medication list at discharge		BAS	BAS, FAS, EFAS
ADDITIONAL PROCEDURE(S)	Administrative information		-	BAS, FAS, EFAS
	Procedure summary information	ANCILLARY OBJECTIVE	-	BAS, FAS, EFAS
	Consumables		-	BAS, FAS, EFAS
	PVI confirmation		-	BAS, FAS, EFAS
STUDY EXIT	Study exit		APS, BAS	APS, BAS, FAS, EFAS
AE	Administrative Information/Adverse Event	ADDITIONAL OBJECTIVE	-	BAS, FAS, EFAS
	Relatedness of the AE		-	BAS, FAS, EFAS
	Description of AE/AEAC		-	BAS, FAS, EFAS
GENERAL FU	Administrative Information		-	BAS, FAS, EFAS
	History of Arrhythmias since the last visit		-	BAS, FAS, EFAS

	Diagnostics		-	BAS, FAS, EFAS
	Symptoms		-	BAS, FAS, EFAS
	Hospitalizations		-	BAS, FAS, EFAS
	Medication List		-	BAS, FAS, EFAS
12MFU VISIT / 12MFU BY PHONE	Administrative Information		-	BAS, FAS, EFAS
	History of Arrhythmias since the last visit	MAIN OBJECTIVE	-	BAS, FAS, EFAS
	Diagnostics		-	BAS, FAS, EFAS
	Symptoms		-	BAS, FAS, EFAS
	Hospitalizations		-	BAS, FAS, EFAS
	Medication List		-	BAS, FAS, EFAS
	AFEQT	ANCILLARY OBJECTIVE	-	BAS, FAS, EFAS

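### SAP 8.7 benchmarks sites and countries by odds ratio on follow-up items that cover only the time since the last visit, so units with equal risk can differ because of their visit schedule

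*SAP*

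**What the plan says.** SAP 8.7 sets one site or country against all others in the BAS. The content is not selective: "Statistical reports (descriptive statistics) will be provided including all parameters from Baseline, First documented procedure, Additional procedure, GFU and 12MFU". AE-form data are left out. The listed outputs are counts and percentages, mean ± SD and "Odds ratio with 95% CI for all available parameters". Time-to-event output, a rule for adding up events across forms, and an allowance for interval length are not mentioned. The stated use is: "These benchmark reports are designed to be used as quality control for the participating sites and to describe country differences".

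The event items on the follow-up forms are interval items:
- SAP 8.1.1, Tables 4 and 5, label the arrhythmia item "History of arrhythmias since last visit: AF" on the visit forms and on the phone form. SAP Appendix B uses "History of Arrhythmias since the last visit" as the table title.
- Protocol 7.2 says of the 12-month contact: "Data to be collected during 12 months FU includes arrhythmia assessment, diagnostics, symptoms, hospitalization and re-ablations occurred since last visit".
- Protocol 3.4 gives the General FU form the same look-back, from the previous visit to the current one, for hospitalisations and cardioversions.

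Visits are unscheduled. Protocol 7.2.1 says that most sites call patients in at around 3 months and that "some sites also see patients at 6 and 12 months after the Phased RFA". SAP 3.1 adds that General FUs also arise from AF re-occurrence or AE-related symptoms. SAP 7.2.3 does not apply the Protocol's visit windows to GFUs.

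**The concern.** The 12MFU event item does not cover the same period in every unit. It spans about 12 months where no interim visit took place, about 9 where the last visit was the 3-month check, and about 6 where there was also a 6-month check. An event before the last General FU belongs on that earlier form and drops out of the 12MFU percentage. The GFU tables have the mirror-image problem: they hold those earlier events, and only for patients who attended.

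An odds ratio on such an item mixes event risk with visit schedule. Because the reports are meant for site quality control and for describing countries, a schedule difference could be read as a difference in performance.

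**Working it through.** SAP 8.7 states no figure to reproduce, so this is an illustration with the same true risk in every unit.

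**Inputs**
- 12-month event probability p = 0.20, the re-ablation rate assumed in SAP 3.3.
- Constant hazard (assumption).
- Visit times independent of events (assumption, relaxed in step 4).
- Total of 1000 patients (Protocol 4.3). With 38 sites and 13 countries (Protocol 3.6), the average is 1000/38 ≈ 26 per site and 1000/13 ≈ 77 per country. Units of 25 and 100 are used below, so 100 is larger than an average country.

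**Step 1: what the 12MFU item records.** With a look-back of L months, P(L) = 1 − 0.8^(L/12).

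| Look-back | Item reads | Odds | OR vs 12 months |
|---|---|---|---|
| 12 months | 20.0% | 0.250 | 1.00 |
| 9 months | 15.4% | 0.182 | 0.73 |
| 6 months | 10.6% | 0.118 | 0.47 |
| 3 months | 5.4% | 0.057 | 0.23 |

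**Step 2: a unit against a mixed rest.** The comparator in 8.7 is all other units, which will have mixed schedules. Protocol 7.2.1 says most sites check at 3 months and some also later. I take 70% last seen at 3 months and 30% at 6; the split is an assumption. The rest then reads 0.7 × 0.1541 + 0.3 × 0.1056 = 0.1395, odds 0.1622.
- Unit with no interim visit: 0.250/0.1622 = 1.54.
- Unit with a 3-month check: 0.182/0.1622 = 1.12.
- Unit with a 6-month check: 0.118/0.1622 = 0.73.

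**Step 3: how often the 95% CI excludes 1.** Wald interval for the log odds ratio, binomial counts, unit against the rest of 1000:

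| Unit | OR | 25 patients | 100 patients |
|---|---|---|---|
| No interim visit | 1.54 | 16% | 37% |
| 3-month check | 1.12 | 5% | 7% |
| 6-month check | 0.73 | 1% | 12% |
| Same mix as the rest | 1.00 | 3% | 5% |

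**Step 4: visits triggered by events.** Suppose half of all events lead to a General FU of their own (assumption), so that the later 12MFU item no longer covers them. The no-interim-visit unit then reads 0.10 and the rest 0.1395/2 = 0.0698. The odds ratio is 0.1111/0.0750 = 1.48. It hardly moves, but with fewer events the interval excludes 1 in about 11% (25 patients) and 22% (100 patients) of cases.

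**Step 5: what the main analysis does.** SAP 8.1.1 and 8.1.2 take the first dated AF event over all forms, counted from the first documented procedure, and use Kaplan-Meier. The look-back of a single form does not enter.

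**The case against.** The strongest reply is that the plan already holds most of the remedy. SAP 7.2.3 sorts GFUs by time period, shows their number and timing, and plans event rates at 3, 6 and 9 months for AF history, re-ablation and hospitalisation. SAP chapter 8 plans rates at 3, 6, 9 and 12 months and points to 8.7 for the country report. SAP 7.2 states that data are to be shown at patient level. Phased RFA re-dos are recorded on the procedure form (Protocol 7.2), and the benchmark reports them under additional procedures whatever the visit schedule; only re-dos with another technology depend on the follow-up forms alone. All of this stands and reduces the practical effect. It does not rescue 8.7, which refers to none of those rates, lists its own outputs and asks for an odds ratio on every parameter.

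A reader might infer four stronger things that the documents do not support.
- **That false signals will be common.** A no-interim-visit unit against a rest uniformly last seen at 6 months has an odds ratio of about 2.1, and its CI excludes 1 in 33% (25 patients) or 74% (100 patients) of cases. But Protocol 7.2.1 describes 3-month checks at most sites, so that contrast is an extreme.
- **That closely followed sites will always look better and phone-only sites worse.** Protocol 4.4.1 notes silent AF and widely varying screening. Closer follow-up may detect more AF, so the net direction for AF history is open.
- **That every comparison in SAP 8.6.2 is distorted.** That section does plan "Group comparison will be provided including non-parametric statistical tests and odds ratios with 95% CI (two-group comparison) for all parameters", but most groups in Appendix D (age, BMI, gender, case type) are not defined by visit schedule. The clear case is the comparison of patients with more than 5 GFUs against the others.
- **That the trial's main result is biased.** Step 5 shows that this mechanism does not reach it.

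**Conclusion.** The point holds for the interval items in SAP 8.7. Followed as written, the section produces odds ratios that depend on visit schedule when true risk is equal. Under the assumed mix they run from about 0.7 to 1.5. Signals are more frequent than nominal mainly for units without interim visits and for larger units.

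The size rests on a constant hazard, the 20% rate and an assumed mix of schedules; the real mix is unknown, and event-triggered visits reduce the number of false signals. The annotated eCRF (SAP Appendix E) is not available, so the look-back is read from item labels and Protocol text. Baseline, procedure and status items are not affected.

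Severity is minor: the benchmark is descriptive and supports no study objective.

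**What to change.** In SAP 8.7:
- Give no odds ratios on items that cover only the time since the last visit.
- For AF re-occurrence, re-ablation and CVD hospitalisation, compare the unit with the rest by the Kaplan-Meier estimate at day 351 (difference with 95% CI) or by a hazard ratio. Cumulate events from the first documented procedure over the GFU, 12MFU and procedure forms, with all BAS patients included. This adopts the event rates already planned in 7.2.3 and chapter 8. Count from the procedure, as chapter 8 does; 7.2.3 counts from discharge and stops at 9 months.
- For cardioversion, Tables 4 and 5 list no follow-up date. Use a patient-level item for any cardioversion since the first documented procedure over all forms, unless a date is available.
- Show the number and timing of visits per unit, and state that differences in AF detection between units remain. With fully reported events, equal-risk units then have an expected ratio of 1; the change cannot correct for unequal detection.
- Keep form-level comparison for status items: medication, EHRA class and AFEQT.

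Apply the same rule in 8.6.2 where groups are defined by visit count (more than 5 GFUs against the others).

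The cost is SAP wording, a little programming and fewer rows in the benchmark table. The dates for AF, re-ablation and admission are already collected, and no AE-form data are needed, so the data-protection exclusion in 8.7 is respected.

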## 8.8 Graphical analysis

Graphical analysis will be provided for final analysis. The graphs will be created using SAS. Predefined graphical analysis will be done for the following topics and strata. Additional graphical analyses can be carried out after database closure.

**Table 13:** Predefined graphical analysis

Target variable	Analysis method	Patients set or strata
Main objective:  AF re-occurrence by study definition during 12 months  Additional analysis: AF re-occurrence with and without considering the "blanking period" of 90 days  AF re-occurrence up to 14 month (end of FU period) after first documented procedure	Kaplan-Meier estimation (time-to-first-event)	
 
• BAS, FAS, EFAS
 
• AF type
 

Additional objective:  Phased RFA procedure safety	Kaplan-Meier estimation (time-to-first-event)	
 
• FAS
 
• Reason for ablation: index, repeated, re-ablation, left Afl
 

Anticoagulation medication before /during/ after/ at 12months FU	Graphical (stacked) bar analysis	
 
• FAS, EFAS
 
• LAAO implantation
 

Analysis of procedure time by 
 
• Site
 
• Operator
 
	Box-whisker plots	
 
• FAS, EFAS
 

Correlation between Anticoagulation and 
 
• INR
 
• ACT
 
• Stroke
 
	Suitable correlation methods	
 
• FAS
 

Correlation between AF re-occurrence and 
 
• BMI
 
• Age
 
	Suitable correlation methods	
 
• BAS, FAS, EFAS
 

COX regression analysis (SAP chapter 8.1.2)	Forest plot (for HR + CI)	
 
• FAS, EFAS
 

Analysis of DAP - by site	Box-whisker plots	
 
• BAS
 

# Appendix A: Table specifications (examples)

Table specification for analysis tables (numbers, metric and dichotomous variables)

Variable	Specification	Format	Nominator (if applicable)	Denominator (if applicable)
Number of patients in APS	All patients that met the criteria of the APS	Integer		
Age		None		
Mean $\pm$ SD, N	mean $\pm$ standard deviation (format: 2 decimal places), number of patients with age values	2 decimal places, Integer		
Median (Q1-Q3)	median and interquartile range in brackets (format: 2 decimal places)	2 decimal places		
5th and 95th Percentile	median and interquartile range in brackets (format: 2 decimal places)	2 decimal places		
Min, Max	minimal and maximal value (format: 2 decimal places)	2 decimal places		
Male gender	percentage of male patients	2 decimal places	male patients	all patients with gender information

## Appendix B: Analysis tables, Study objectives and Analysis sets

eCRF SEGMENTS	eCRF CHAPTERS/ANALYSIS TABLES	STUDY OBJECTIVES	ANALYSIS SETS FOR INTERIM ANALYSIS	ANALYSIS SETS FOR FINAL ANALYSIS
BASELINE	Enrolment		APS, BAS	APS, BAS, FAS, EFAS
	Indication/Admission		APS, BAS	APS, BAS, FAS, EFAS
	Demographics		BAS	BAS, FAS, EFAS
	History of CVD		BAS	BAS, FAS, EFAS
	History of AF		BAS	BAS, FAS, EFAS
	Symptoms		BAS	BAS, FAS, EFAS
	Concomitant Diseases		BAS	BAS, FAS, EFAS
	Diagnostics		BAS	BAS, FAS, EFAS
	Medications List		BAS	BAS, FAS, EFAS
	AFEQT		BAS	BAS, FAS, EFAS
	Anticoagulation (before/during first documented procedure)	ANCILLARY OBJECTIVE	BAS	BAS, FAS, EFAS
FIRST DOCUMENTED PROCEDURE	Administrative information		APS, BAS	APS, BAS, FAS, EFAS
	Procedure summary information	ANCILLARY OBJECTIVE	BAS	BAS, FAS, EFAS
	Consumables		BAS	BAS, FAS, EFAS
	PVI confirmation		BAS	BAS, FAS, EFAS
	Hospital discharge		APS, BAS	APS, BAS, FAS, EFAS
	Medication list at discharge		BAS	BAS, FAS, EFAS
ADDITIONAL PROCEDURE(S)	Administrative information		-	BAS, FAS, EFAS
	Procedure summary information	ANCILLARY OBJECTIVE	-	BAS, FAS, EFAS
	Consumables		-	BAS, FAS, EFAS
	PVI confirmation		-	BAS, FAS, EFAS
STUDY EXIT	Study exit		APS, BAS	APS, BAS, FAS, EFAS
AE	Administrative Information/Adverse Event	ADDITIONAL OBJECTIVE	-	BAS, FAS, EFAS
	Relatedness of the AE		-	BAS, FAS, EFAS
	Description of AE/AEAC		-	BAS, FAS, EFAS
GENERAL FU	Administrative Information		-	BAS, FAS, EFAS
	History of Arrhythmias since the last visit		-	BAS, FAS, EFAS

	Diagnostics		-	BAS, FAS, EFAS
	Symptoms		-	BAS, FAS, EFAS
	Hospitalizations		-	BAS, FAS, EFAS
	Medication List		-	BAS, FAS, EFAS
12MFU VISIT / 12MFU BY PHONE	Administrative Information		-	BAS, FAS, EFAS
	History of Arrhythmias since the last visit	MAIN OBJECTIVE	-	BAS, FAS, EFAS
	Diagnostics		-	BAS, FAS, EFAS
	Symptoms		-	BAS, FAS, EFAS
	Hospitalizations		-	BAS, FAS, EFAS
	Medication List		-	BAS, FAS, EFAS
	AFEQT	ANCILLARY OBJECTIVE	-	BAS, FAS, EFAS

## Appendix C: Subgroup analysis

Predefined subgroups (V1.0)

Subgroup description	Analysis set, additional inclusion or exclusion criteria	Tables and scope for analysis
Indication to schedule Phased RFA: Paroxysmal AF	FAS, EFAS incl.: --- excl.: ---	Baseline First documented procedure Additional procedure 12MFU
Indication to schedule Phased RFA: Persistent AF	FAS, EFAS incl.: --- excl.: ---	Baseline First documented procedure Additional procedure 12MFU
Indication to schedule Phased RFA: Longstanding persistent AF	FAS, EFAS incl.: --- excl.: ---	Baseline First documented procedure Additional procedure 12MFU
Successful first documented procedure	FAS, EFAS incl.: --- excl.: ---	Baseline First documented procedure Additional procedure 12MFU
Non-successful first documented procedure	FAS, EFAS incl.: --- excl.: ---	Baseline First documented procedure Additional procedure 12MFU
First documented procedure: PVAC GOLD solely	FAS, EFAS incl.: Phased RFA catheters = PVAC GOLD, general number if catheters used = 1 excl.: adjunctive devices used during the procedure, disregarding sheaths used	First documented procedure Additional procedure GFU 12MFU
First documented procedure: PVAC GOLD + other catheters	FAS, EFAS incl.: Phased RFA catheters = PVAC GOLD, general number if catheters used > 1, additional Phased catheter used (MAAC, MASC and/or Other) excl.: adjunctive devices used during the procedure, disregarding sheaths used	First documented procedure Additional procedure GFU 12MFU
First documented procedure: Phased RFA catheter solely	FAS, EFAS incl.: Phased RFA catheters used, general number if catheters used = 1 excl.: adjunctive devices used during the procedure, disregarding sheaths used	First documented procedure Additional procedure GFU 12MFU
First documented procedure: Phased RFA catheter + adjunctive devices	FAS, EFAS incl.: Phased RFA catheters = PVAC GOLD, general number if catheters used > 1, additional Phased catheter used (MAAC, MASC and/or Other), adjunctive devices used during the procedure excl.: ---	First documented procedure Additional procedure GFU 12MFU
Procedure: Patients with multiple procedures	FAS, EFAS	Baseline First documented procedure Additional procedure

	incl.: patients with > 1 documented procedure excl.: ---	GFU 12MFU
Baseline:  Patient with AF surgery or ablations in history	FAS, EFAS  incl.: prior AF surgery, status post ablation (endocardial, epicardial, Catheter PV, Phased RF, 3D RF or Other ablation technologies) excl.: ---	Baseline First documented procedure Additional procedure GFU 12MFU
Baseline:  Patient without AF surgery or ablations in history	FAS, EFAS  incl.: no prior AF surgery, no status post ablation (endocardial, epicardial, Catheter PV, Phased RF, 3D RF or Other ablation technologies) excl.: ---	Baseline First documented procedure Additional procedure GFU 12MFU
Baseline:  Reveal implanted patients	FAS, EFAS  incl.: ICM implantation - Reveal XT, Reveal LINQ or other excl.: ---	Baseline First documented procedure Additional procedure GFU 12MFU
First documented procedure:  Anticoagulation in patients with LAAO	FAS, EFAS  incl.: LAAO implantation, anticoagulation medication prior first documented procedure excl.: ---	Baseline First documented procedure 12MFU
First documented procedure:  patients with LAAO	FAS, EFAS  incl.: LAAO implantation excl.: anticoagulation medication prior first documented procedure	Baseline First documented procedure 12MFU
Patients with administrated at least one antiarrhythmic drug (except beta-blocker)	FAS, EFAS  incl.: patients with $\geq 1$ antiarrhythmic medication (except beta-blocker) at any time of this study excl.: ---	Baseline First documented procedure GFU 12MFU
Patients without antiarrhythmic drug therapy	FAS, EFAS  incl.: no antiarrhythmic medication at any time of this study excl.: ---	Baseline First documented procedure GFU 12MFU
First documented procedure:  Patients with discontinued oral anti-coagulation before the procedure	FAS, EFAS  incl.: patients with oral anticoagulation prior to scheduled phased RFA and discontinued before first documented procedure excl.: ---	First documented procedure GFU 12MFU
First documented procedure:  Patients with oral anticoagulation before the procedure	FAS, EFAS  incl.: patients with oral anticoagulation prior to scheduled phased RFA and not discontinued before first documented procedure excl.: ---	First documented procedure GFU 12MFU
Patients lost to 12 month FU	APS, BAS  incl.: patients w/o 12MFU excl.: ---	Baseline First documented procedure Additional procedure GFU 12MFU

